16. SUBJECT PROTECTION

Data will be de-identified on forms and in the clinical database, and subjects will be identified only by a code or subject number. All information and data sent to ConforMIS or designee concerning patients or their participation in this study will be considered confidential, and confidentiality shall be observed by all parties involved at all times during the study. All data used in analysis and reports will be used without identifiable reference to the subject. All data will be secured against unauthorized access. The Investigator and investigative site will be responsible for compliance with all local privacy regulations.

17. ETHICAL CONSIDERATIONS

The protocol and Informed Consent Form must be approved by a central IRB or the IRB/IEC for the institution where the study is conducted. Each subject shall give informed consent in a form and manner that meets all IRB/IEC requirements. All subjects must be informed that the device is available commercially and that participation in the clinical study is not required for them to be treated with the device. Investigators shall agree to conduct the study in compliance with the provisions of the Declaration of Helsinki and with ICH/GCP Standards.

In compliance with the Food and Drug Administration Amendments Act of 2007 (FDAAA), this study will be listed in www.clinicaltrials.gov.

18. REPORTS

A final study report shall be prepared and provided to all investigative sites for submission to their IRB/IEC. The final study report will be made a permanent record in the ConforMIS document control system.

3.0 AB	14 October 2015	[name]	
Updated [name]'s job title.
 
Under Study Design (section 3), surgical approach was updated to allow for other approaches.
 
Changed the name of section 7.1 from "Primary Endpoint" to "Primary Endpoints".
 
In section 7.1, Primary Endpoints, further detailed the components comprising the ALF score.
 
Updated section 8, Site Selection, to section 9, in turn correcting an overall issue with the numbering throughout the remainder of the protocol.
 
Updated AE language (section 12) so that only AEs that are at least possibly related to the device or procedure are captured in the first 90 days post-op.
 
Updated Appendix A, combining Onsite and Remote Follow Up and altering the spacing/positioning.
 
Updated Appendix B to clarify instructions.
 
Added Appendix D, CONSORT Data Reporting Guidelines, and an explanation in Section 8, Inclusion/Exclusion Criteria, how sites will log all patients considered for the study.
 
Updated the Table of Contents.

4.0 AC	30 April 2016	[name]	
Updated versioning to 4.0 AC in all headers and footers and protocol signature page.
 
Under Study Design (section 3), surgical approach was defined and updated to allow for only medial parapatellar or subvastus approach.
 
Under schedule of evaluation section, for concomitant medications, added the word “(optional)” for all time points except for screening.
 
Under Appendix A, added an “*” to radiographic evaluation (long leg) row to indicate that this is to occur at the 90 Days or 180 Days visit.
 
Updated Functional Testing Worksheet in Appendix B to make changes to CRF, including shading and a typo.
 
Appendix C updated SAS version to match main protocol

5.0 AD	27 March 2017	[name]	
Updated the title from: “A Prospective, Randomized, Multicenter Study to Evaluate the ConforMIS iTotal (CR) Knee Replacement System versus Off-the-Shelf Replacement” to “A Prospective, Multicenter Study to Evaluate Functional Outcome After Knee Replacement”
 
Throughout document, oxford comma used
 
Updated ConforMIS address
 
Added ConforMIS internal use ID
 
Deleted randomization throughout the protocol
 
Deleted the use of patient specific instrumentation.
 
Updated the study design to reflect no randomization.
 
Deleted double blinding. Only functional tester is blinded. Updated throughout protocol.
 
Updated N

		
Updated language for economic study. Only sites who are contracted with ConforMIS will take part.
 
Updated timed “Get-up and Go” test definition to clarify the length of the walk.
 
Updated 8 meter walk with the correct reference. National Institutes of Health instead of McCarthy.
 
Updated the Timed Up and Down Stairs Test to include a minimum of 4 steps in a flight of stairs.
 
Deleted the patient reported outcomes as a primary endpoint.
 
Added KSS as a secondary endpoint. Updated statistical analyses with KSS information.
 
Updated exclusion criteria to provide clarity. Deleted “Other lower extremity surgery within 1 year” to “Lower extremity surgery (orthopaedic or ligament injury) on either limb to the hip, ankle, feet occurring or expected to occur within 1 year of surgery on the evaluated knee”
 
Updated exclusion criteria to provide clarity. Changed “Contralateral knee replacement surgery within the past 6 months” to “Contralateral knee replacement occurring or expected to occur within 6 months of surgery on the evaluated knee”
 
Added instructions on how a site will consecutively enroll subjects.
 
Administrative changes to provide clarity.
 
Clarified Safety reporting. Added phone number and email along with instructions of what needs to be included in the communications to the sponsor and the IRB.
 
Updated efficacy analysis

--	--	---

			Updated the sample size determination paragraph Updated Appendix A to reflect changes
--	--	--	--

20. APPENDIX A – Schedule of Evaluations

Evaluation	Screening/ Pre-Op	Surgery	90 Days Follow-up	180 Days Follow-up	Year 1, 2, 5 Follow-up	Year 3, 4, 6, 7, 8, 9 Follow-up	Year 10 Follow-up
Visit window	Up to 4 months prior to surgery	N/A	± 14 days	± 21 days	± 2 months	± 3 months	± 4 months
Inclusion/Exclusion Criteria	X						
Subject Information & Medical History	X						
Pain Medications & Concomitant Medications‡	X	X	X	X	X		X
Knee Society Score (KSS)	X		X	X	X		X
Knee Injury & Osteoarthritis Outcome Score (KOOS)	X		X	X	X		X
Functional Testing	X		X	X	X		X
Radiographic Evaluation *	X		X†	X†			
Surgical & Discharge Summary		X					
Adverse Events & Serious Adverse Events		X	X	X	X	X	X
Follow Up			X	X	X	X	X
Subject Disposition							X ⁺

‡ The collection of Concomitant Medications is optional after the Pre-operative visit

[figure not shown]
*Radiographic evaluation includes: Knee x-ray 3 views- AP, lateral, sunrise or Merchant; Long Leg x-ray (full length film with full weight bearing)- AP view

†Post-operative radiograph can be performed at 90 or 180 days depending on hospital standard

+ Subject Disposition to be completed either at the 10 year visit or when the subject withdraws from the study

21. APPENDIX B – Functional Testing Instructions

Timed Get Up and Go Test

Equipment needed: Arm chair, tape measure, tape, stopwatch, and cone

[figure not shown]
Test Set Up:

1. Place a chair in an area with adequate space for the patient to walk and turn around.
2. Measure 30.5 cm (12 inches; 1ft) in front of the chair and place a piece of tape there.
3. From the piece of tape, measure 3 meters (118 inches; 9ft & 10 in) and place another piece of tape at the end.
4. Place the cone on top the piece of tape at the 3 meter mark (ensure the middle of the cone is aligned with the center of the tape).

Test Instructions:

1. The subject should begin the test sitting comfortably in the chair with their feet on the ground. The subject is allowed to use the arm rests during the sit and stand movements. The subject is allowed to use assistive devices such as a cane or walker. If the subject uses the arm rests or an assistive device, please record this on the form.
2. Instruct the subject using the following command:
 - “On the word ‘GO’ you will stand up, walk to the cone, walk around the cone, and then walk back towards the chair to sit down. Walk as quickly as you feel safe.”
3. Stopwatch instructions:
 - Start timing when you say “GO.”
 - Stop timing when the subject is completely seated (same as starting position).
4. There will be 3 individually timed tests.

8 Meter Walk

Equipment needed: Stopwatch, cone, tape measure, and tape

Test Set Up:

1. Place a piece of tape as a starting point in an area with adequate space for the patient to walk and turn around.
2. Measure 4 meters from that point and place a second piece of tape at that location.

4 meters =

[figure not shown]
13.12 Feet
157.48 Inches
13 Feet and 1.48 inches
400 Centimeters
4.37 Yards
2.35 Smoot

3. Place the cone on top the piece of the second piece of tape.

Test Instructions:

1. The subject should stand at the first piece of tape.
2. Instruct the subject using the following command:
 - “On the word ‘GO’ you will walk to the cone, walk around the cone, and then walk back towards first piece of tape. Walk as quickly as you feel safe.”
3. Stop watch instructions:
 - Start timing when you say “GO.”
 - Stop timing when the subject’s second foot touches the first piece of tape.
4. There will be 3 individually timed tests.

Timed Up & Down Stairs Test

Equipment needed: Stopwatch, Flight of Stairs

Test Set Up:

1. Count the number of steps and record this on the form. Count the steps in one direction. For example, in the diagram above, there are 5 steps. The flight of stairs used in this test must have a minimum of 4 stairs.
2. If possible, please use the same flight of stairs for all subjects.

Test Instructions:

1. The subject should stand at the bottom of the flight of stairs.
2. Instruct the subject using the following command:
 - “I am going to ask you to stand at the bottom of the stairs so that your first step is up. My commands will be ‘ready, set, GO’. Then you are going to walk as quickly as you feel safe and comfortable to the top of the stairs, turn around, and come back down. You may use the rail, but if you can go without the rail, please try to do so.”
3. Stop watch instructions:
 - Start timing when you say “GO.”
 - Stop timing when the subject’s second foot touches the landing at the bottom of the stairs.
4. At the end of each test, ask the subject about their pain level during the test, their confidence, and their comfort in completing another trial.
5. If the subject answers “no” concerning their comfort in completing the stairs, then do not have them attempt the stairs again.
6. There will be 3 individually timed tests if the subject feels comfortable completing each test.

Time Point (check one):  Pre-op  90 Days  180 Days  Year 1  Year 2  Year 5  Year 10														
Trial	Get Up & Go Time (mm:ss.ms)	Get Up & Go Rest Time (mm:ss.ms)	Arms Used?	Circle Pain Level After Each Trial										
1	_____ : _____ . _____	_____ : _____ . _____	Y N	0	1	2	3	4	5	6	7	8	9	10
2	_____ : _____ . _____	_____ : _____ . _____	Y N	0	1	2	3	4	5	6	7	8	9	10
3	_____ : _____ . _____	_____ : _____ . _____	Y N	0	1	2	3	4	5	6	7	8	9	10
Did the subject require a rest between the Chair and Walking activities?				Y	N									
Trial	Walking Time (mm:ss.ms)	Walking Rest Time (mm:ss.ms)	Circle Pain Level After Each Trial											
1	_____ : _____ . _____	_____ : _____ . _____	0	1	2	3	4	5	6	7	8	9	10	
2	_____ : _____ . _____	_____ : _____ . _____	0	1	2	3	4	5	6	7	8	9	10	
3	_____ : _____ . _____	_____ : _____ . _____	0	1	2	3	4	5	6	7	8	9	10	
Did the subject require a rest between the Walking and Stairs activities?				Y	N									
Trial	Stairs Time (mm:ss.ms)	Stairs Rest Time (mm:ss.ms)	Rails Used?	Circle Pain Level After Each Trial										
1	_____ : _____ . _____	_____ : _____ . _____	Y N	0	1	2	3	4	5	6	7	8	9	10
How confident were you in your ability to complete the Stairs during that trial?				Very	Somewhat	Not Very	Not At All							
Do you feel comfortable completing the Stairs a second time?				Y	N									
2	_____ : _____ . _____	_____ : _____ . _____	Y N	0	1	2	3	4	5	6	7	8	9	10
How confident were you in your ability to complete the Stairs during that trial?				Very	Somewhat	Not Very	Not At All							
Do you feel comfortable completing the Stairs a third time?				Y	N									
3	_____ : _____ . _____	_____ : _____ . _____	Y N	0	1	2	3	4	5	6	7	8	9	10
How confident were you in your ability to complete the Stairs during that trial?				Very	Somewhat	Not Very	Not At All							

Number of Steps (in staircase): _____

Observations: _____

22. APPENDIX C – U.S. Economic Sub-Study

A cost comparison between the groups will be performed. Each site will obtain the Uniform Billing (UB) forms from their billing department. These forms will have the following information for analysis:

- Length of stay
- Blood transfusions throughout the stay (number of units and type of transfusions)
- Patient discharge disposition
- Patient comorbidities
- Readmission to hospital and 30-day readmission rate
-

Additionally, in the case report forms, the following information will be collected for analysis:

- Number of trays used
- Instances of compromised tray sterility
- Procedure and device related adverse events

Primary outcome:

Economic Outcomes as measured by collected hospital data and Uniform Billing (UB) forms

Statistics:

All statistical processing will be performed using SAS® Version 9.3 or later unless otherwise stated.

No imputations will be made for missing observations. Continuous variables will be summarized with sample size, mean, standard deviation, median, minimum, maximum, and 95% confidence intervals, as appropriate. Categorical variables will be summarized with frequency counts, percentages, and 95% confidence intervals, as appropriate.

Demographic Evaluations & Cost Analysis

Demographic variables (age, gender, ethnicity, and race) will be recorded in the database and summarized using descriptive statistics. For continuous variables, comparisons between treatment groups will be conducted with an analysis of variance (ANOVA). A Chi-square test will be used for testing categorical variables.

23. APPENDIX D – CONSORT Data Reporting Guidelines

CONSORT 2010 Flow Diagram

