3. The Timed Up and Down Stairs Test (TUDS) is a functional test that “demands more balance, coordination, strength and muscle control than walking demands” (Lepage 1998; Zaino 2004). This test will involve a stopwatch and a flight of stairs with rails. A usual set of stairs is 12 steps that are 18cm high with a depth of 28cm. The flight of stairs used during testing must have a minimum of 4 steps. The subject will stand at the bottom of the stairs. The test administrator will voice the command “go” and start the stopwatch. The subject will walk as quickly as they feel safe and comfortable to the top of the stairs, turn around, and come back down the stairs. Once the subject is safely back down with both feet back on the landing, the test administrator will stop the stopwatch. The subject may use the rail, but the preference is to do this test without the use of a rail. Assistive devices are allowed only if the subject does not feel safe or cannot do this test without the assistive devices. The test administrator will take note if the rail or an assistive device was used during the test. Again, the subject will be instructed to move as quickly as they

feel safe and are comfortable. There will be 3 timed trials. The average will be used for data analysis.

The Aggregated Locomotor Function (ALF) score is formed by summing the mean of the above three timed tests (McCarthy 2004). Suggested instructions are located in Appendix B.

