7. STUDY ENDPOINTS

7.1. Primary Endpoints

The primary functional endpoint will be measured by the Aggregated Locomotor Function (ALF) score (TUG, 8 Meter Walk, and TUDS activities) and/or its components at 1 Year post-implantation.

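### A subject who attends Year 1 but completes no stair trial has no ALF, and the only fallback, LOCF, would not count that inability as a poor outcome

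*Combined protocol and SAP*

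**What the plan says.** All references are to the combined protocol and SAP.

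- **Endpoint.** Section 7.1 makes the ALF "and/or its components at 1 Year post-implantation" the primary endpoint. Section 5 defines it: "The Aggregated Locomotor Function (ALF) score is formed by summing the mean of the above three timed tests", that is, TUG, 8 Meter Walk and Timed Up and Down Stairs (TUDS).
- **Stair scoring, main text.** Section 5, item 3: "There will be 3 timed trials. The average will be used for data analysis".
- **Stair scoring, Appendix B.** "There will be 3 individually timed tests if the subject feels comfortable completing each test". The comfort question comes after a trial ("At the end of each test, ask the subject about their pain level during the test" opens that instruction). If the answer is no, "then do not have them attempt the stairs again".
- **Worksheet, Appendix B.** It has fields for trial times, rest times, rail use, pain and confidence, yes/no items on willingness to do a second and a third stair trial, and a free-text line. It has no code for a test that was not done at all.
- **Analysis, Section 15.** The primary analysis is an ANCOVA of the change from baseline to Year 1. Missing efficacy data are imputed by LOCF, with no exception. The FAS holds everyone whose procedure was completed. The listed per-protocol exclusions concern eligibility, attendance, visit window and contralateral procedures, not inability to perform a test.

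**The concern.** A sum of three means needs all three. A subject who comes to Year 1, walks, and cannot or will not start the stairs gives an observed result, and a bad one. The plan gives that result no value, so by default it falls under the missing-data sentence and takes a value from a visit at which the subject could still climb. Section 1 explains that the functional tests were added because questionnaires can fail to show functional worsening. Replacing a functional failure with an earlier success works against that purpose.

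The between-arm comparison is at stake if inability is unequal. Equal rates cannot be taken for granted: Section 3 allocates by alternating groups of ten without randomisation, and only the functional tester is blinded.

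The second gap is smaller. Main text and appendix differ on how many stair trials there are, and neither says how TUDS is formed from one or two.

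**Working it through.** **1. What happens to each pattern of stair trials at an attended Year 1 visit**

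| Trials completed | TUDS and ALF under the text | Gap |
|---|---|---|
| 3 | Mean of three; ALF exists | None |
| 1 or 2 | At least one time exists; ALF can be computed | No rule for the mean |
| 0 | No TUDS, hence no ALF | Only LOCF applies |

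In the zero-trial row, the value used depends on history:

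- With a 90- or 180-day result, that earlier result is used.
- With only baseline, the change is zero.
- With no baseline ALF either, the subject leaves the ANCOVA.

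The plan does not say whether LOCF acts on TUDS alone or on the whole ALF. In the second case the observed Year 1 TUG and walk are also set aside in the ALF. The subject stays in the FAS and, under the listed criteria, can stay in the per-protocol set too.

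**2. The plan's own figure**

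Section 15 states power above 80% with 225 to 300 per arm. Effect size, SD, alpha and sidedness are not given, so this can be neither reproduced nor refuted. Assuming two-sided alpha 0.05, the standardised difference detectable with 80% power is (1.96 + 0.84) × √(2/n):

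- n = 225: 2.80 × √(2/225) = 0.264 SD
- n = 300: 2.80 × √(2/300) = 0.229 SD

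**3. Size of the possible misstatement**

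Let W be how many SD worse an unable subject should score than the value LOCF supplies, and u the difference between arms in the proportion unable. The mean difference is then misstated by about W × u. Both W and u are assumptions; neither is in the documents.

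| W | u | Shift (SD) | Share of 0.264 |
|---|---|---|---|
| 2 | 1% | 0.02 | 8% |
| 2 | 3% | 0.06 | 23% |
| 2 | 5% | 0.10 | 38% |
| 3 | 1% | 0.03 | 11% |
| 3 | 5% | 0.15 | 57% |

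**4. Simulation check**

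This used 225 per arm, 1,500 runs, normal times with SD 1 (lower is better) and a true benefit of 0.264 SD among those who perform the test. The carried value was drawn from the performers' distribution in the same arm. LOCF was tested by t-test, and the worst observed score by Mann-Whitney.

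| Unable, better v other arm | LOCF: difference, power | Worst score: difference, power |
|---|---|---|
| 2% v 2% | −0.265, 80% | −0.259, 75% |
| 6% v 2% | −0.264, 80% | −0.131, 43% |
| 2% v 6% | −0.264, 80% | −0.374, 89% |

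LOCF returns the same answer whichever arm has more inability. In the second row the estimates differ by 0.264 − 0.131 = 0.133 SD, close to step 3 at W = 3 (3 × 0.04 = 0.12). With equal rates the choice hardly matters.

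**The case against.** The strongest reply is that the gap is narrow.

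- **The stop rule follows a trial.** A reader might infer that the Appendix B instruction to stop leaves a subject without an ALF. It does not. Comfort is asked after a completed trial, so everyone stopped by that rule has at least one stair time. The undefined ALF comes from the definition in Section 5 together with the LOCF sentence in Section 15. This objection stands.
- **Declining a repeat is recorded.** The yes/no items capture it. Only a coded reason for doing no trial is absent. This stands too.
- **Few subjects may be affected.** Rails may be used, and on aids Section 5 says "Assistive devices are allowed only if the subject does not feel safe or cannot do this test without the assistive devices". The flight may have as few as four steps, and exclusions 13 and 19 remove some at-risk subjects before surgery. All of this lowers the rate but does not bring it to zero, and none of it supplies a score.
- **The components remain.** Section 7.1 leaves TUG and the walk analysable in their own right. That is true, but it does not repair the ALF or TUDS.
- **LOCF is not always flattering.** If baseline is the only earlier value, zero change scores as no improvement. That is fair, but it still cannot register a decline.
- **Averaging completed trials is the natural reading.** Agreed, and it should be written down.

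**Conclusion.** The point holds. For a subject with no stair trial at an attended Year 1 visit, the plan gives no ALF, and its only rule would put an earlier result or zero change in place of an observed inability. This goes beyond missing detail, because following the plan as written produces the unwanted value. The plan does not itself class inability as missing; that is the default effect of an LOCF rule without exceptions.

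A reader might go further and infer that the primary comparison is biased. The documents do not support that. They give no rate of inability in either arm. Bias in the comparison arises mainly if the rates differ, and it then favours the arm with more inability.

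The size is illustrative: 0.02 to 0.10 SD for arm differences of 1 to 5 points, or 8% to 38% of 0.264 SD. It rests on an assumed 2 SD penalty, two-sided 5% alpha, 80% power and 225 per arm. The low end is negligible. No figure in the plan is shown to be wrong.

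The difference between three stair trials in Section 5 and one or two in Appendix B is a separate, minor inconsistency that needs reconciling.

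**What to change.** 1. Add to the worksheet, for each test, a coded reason for not done: unable, unsafe, declined, other.
2. State in Section 15 that LOCF does not apply to knee-, pain- or safety-related inability at an attended visit.
3. Prespecify a rank-based ANCOVA of ALF and of TUDS with these subjects ranked worst, as a supportive analysis beside the planned ANCOVA.
4. If a numeric worst value is used, take it from comparable staircases (same site or same step count). Section 5 allows any flight of four steps or more, and Appendix B asks for one common flight only where possible, so a study-wide worst time would partly measure the staircase. Let the value replace TUDS only, and keep the observed TUG and walk in the ALF.
5. Report and compare by arm the proportion completing the stairs.
6. Reconcile Section 5 with Appendix B on scoring: average TUDS over completed trials, with a first-trial-only sensitivity analysis, since everyone who completes any stair trial has a first one.

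The cost is one worksheet field per test, a few sentences of SAP text and some extra analysis. The downside is that the result becomes somewhat sensitive to how inability is ranked or valued, which is why the ranked analysis stands beside the planned one.

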2. DEVICE DESCRIPTION

The iTotal CR Knee Replacement System (hereafter referred to as the "iTotal CR") is a patient-specific tricompartmental faceted posterior cruciate ligament (PCL) retaining knee replacement system. The iTotal CR is a semi-constrained cemented knee implant which consists of a femoral, tibial and patellar component.

Using computed tomography (CT) and a combination of proprietary and off-the-shelf software a patient-specific implant is designed, that best meets the geometric and anatomic requirements of the specific patient. The femoral component is manufactured from cobalt chromium molybdenum

("CoCrMo") alloy. The tibial component includes a metal tray manufactured from CoCrMo alloy and polyethylene inserts. The polyethylene inserts may be manufactured from either UHMWPE or a highly cross-linked Vitamin E infused polyethylene (iPoly XE™). The patellar component is also manufactured from either UHMWPE or from a highly cross-linked Vitamin E infused polyethylene (iPoly XE).

Several key features of the iTotal CR are listed below:

- Disposable, patient-specific instrumentation
- Simple, reproducible surgical technique
- Potential for less post-operative pain and shorter post-operative recovery time

The control will be one of three off-the-shelf CR systems:

- DePuy Synthes: Attune
- Zimmer: Persona
- Stryker: Triathlon

For all procedures, the patella will be resurfaced using the patella implant available through the respective manufacturer.

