4. ECONOMIC SUBSTUDY

This study will include a prospective economic analysis of US sites if contracted by the Sponsor. Please refer to Appendix C for complete description.

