11. SCHEDULE OF EVALUATIONS BY VISIT

A table displaying the Schedule of Evaluations is in Appendix A. Regardless of treatment arm assigned, subjects will complete each visit in the schedule of evaluations below.

11.1. **Preoperative Visit (Up to 4 months prior to Surgery)**

Many of the screening assessments required to ensure subject eligibility are also considered the pre-operative assessments. The results of the assessments will be captured on the following Screening/Pre-operative Case Report Forms:

- SUBJECT INFORMATION / MEDICAL HISTORY
- CONCOMITANT MEDICATIONS
- PAIN MEDICATIONS
- INCLUSION/EXCLUSION CRITERIA
- KNEE SOCIETY SCORE (Surgeon portion)

The subject will complete the following function tests and questionnaires to assess pain and function as part of their preoperative assessment:

- THE KNEE INJURY AND OSTEOARTHRITIS OUTCOME SCORE (KOOS)
- KNEE SOCIETY SCORE (Subject portion)
- TIMED "GET UP AND GO"
- 8 METER WALK
- TIMED UP AND DOWN STAIRS

X-rays:

- 3 views – AP, lateral, sunrise or Merchant
- Three foot standing x-ray (full length, full weight-bearing film): AP view

11.2. **Surgery Visit (Day 0)**

The Investigator will surgically implant either the iTotal CR in compliance with the ConforMIS surgical training and Instructions for Use, or the off-the-shelf TKR per their surgical training and the manufacturer's Instructions for Use.

The site will complete the following Case Report Forms:

- SURGICAL SUMMARY
- DISCHARGE SUMMARY
- CONCOMITANT MEDICATIONS (optional)
- PAIN MEDICATIONS
- ADVERSE EVENTS (if any occur during surgery through discharge from hospital)

X-rays: None

11.3. **90 Days Follow-up Visit (\pm 14 days)**

At the 90 days follow-up visit, the Investigator or study staff will perform a post-operative knee assessment and identify any adverse events that have occurred since the subject was discharged from the hospital. The site will also collect the Uniform Billing (UB) form from their billing department if contracted with the Sponsor to participate in the Economic Sub-study.

The site will complete the following Case Report Forms:

- FOLLOW UP
- KNEE SOCIETY SCORE (Surgeon portion)

- CONCOMITANT MEDICATIONS (optional)
- PAIN MEDICATIONS
- ADVERSE EVENTS (if any)
 - REVISION FORM (if necessary)

The subject will complete the following function tests and questionnaires to assess post-operative pain and function:

- THE KNEE INJURY AND OSTEOARTHRITIS OUTCOME SCORE (KOOS)
- KNEE SOCIETY SCORE (Subject portion)

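### Appendix C promises a cost comparison but names neither the planning CT described only for iTotal nor implant cost; leaving out the CT understates iTotal cost

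*Combined protocol and SAP*

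**What the plan says.** Section 4 makes the economic work optional and local: "This study will include a prospective economic analysis of US sites if contracted by the Sponsor". Appendix C gives its aim: "A cost comparison between the groups will be performed".

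Appendix C draws its inputs from two sources.

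- **Billing forms**, introduced by "These forms will have the following information for analysis": duration of stay, transfusions, where the patient is discharged to, comorbidities, and "Readmission to hospital and 30-day readmission rate".
- **Case report forms**: "Number of trays used", compromised sterility of trays, and adverse events related to the procedure or device.

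The primary outcome of the sub-study is worded broadly: "Economic Outcomes as measured by collected hospital data and Uniform Billing (UB) forms". On timing, Section 11.3 says under the 90-day visit that "The site will also collect the Uniform Billing (UB) form from their billing department", for contracted sites. It does not say which encounters the form must cover. The statistics paragraph of Appendix C specifies descriptive summaries, ANOVA and chi-square tests, and gives no rule for turning resources into costs.

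Section 2 describes how the iTotal implant is made: "Using computed tomography (CT) and a combination of proprietary and off-the-shelf software a patient-specific implant is designed". It lists three off-the-shelf control systems and mentions no CT for them. The imaging in Sections 10 and 11 and in Appendix A consists of x-rays only.

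**The concern.** A cost comparison between two implants should count the inputs that differ because of the choice of implant. Here two such inputs can be read from the protocol itself: a design CT in one arm, and a patient-specific product against a stock product. Neither is named. The list does name trays and tray sterility, where a system with disposable instruments could plausibly show a saving. A possible iTotal saving is therefore set down for collection, while a cost that only iTotal is described as incurring is not.

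At stake is any statement on relative cost from the sub-study. Leaving out a cost that arises in one arm only is a systematic error, so more subjects would not reduce it. Because the components are not fixed in advance, they could also be chosen after the data have been seen.

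**Working it through.** The plan gives no cost figure, so there is none to reproduce. The check sets the sections side by side and then works out the direction by algebra.

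**1. Is each arm-specific input captured?**

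| Input | iTotal | Off-the-shelf | Named in Appendix C | Visit or form described as recording it |
|---|---|---|---|---|
| Planning CT | Yes (Section 2) | None described | No | None |
| Implant cost | Patient-specific product | Stock product | No | None |
| Trays, tray sterility | Disposable instruments (Section 2) | Not described | Yes | Case report forms |

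The contents of the case report forms are mostly not shown in the protocol. The last column therefore says only that nothing is described as recording the item.

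**2. Direction of the error.** Define:

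- C = cost of the planning CT
- P1 = price of the iTotal implant with its instruments
- P0 = price of the off-the-shelf implant with its instruments
- D = true cost difference per subject, iTotal minus off-the-shelf
- d = the difference measured when CT and implant are both left out

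Then d = D - [C + (P1 - P0)], and iTotal is understated by U = C + (P1 - P0).

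- *CT alone:* U = C, which is above zero at any CT price. This part favours iTotal.
- *Implant alone:* U = P1 - P0. The documents give neither price, so the sign is unknown.
- *Both:* U is zero when P1 - P0 = -C. The net omission favours iTotal unless its implant is cheaper than the comparator by more than the cost of one CT.

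**3. Illustration with assumed values.** None of these comes from the documents: C from 200 to 1,000 USD, and P1 - P0 from -1,000 to +2,000 USD.

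- Lowest: 200 + (-1,000) = -800 USD per subject
- Highest: 1,000 + 2,000 = +3,000 USD per subject
- Equal implant prices: +200 to +1,000 USD per subject, the CT alone

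The range crosses zero only because the implant term can be negative.

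**4. Reach.** The error applies to iTotal subjects at contracted US sites. Section 3 places the trial in the UK and Germany as well, and those subjects are outside the sub-study. Economic outcomes are not among the primary or secondary endpoints in Section 7.

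**The case against.** The strongest reply is that these costs are unspecified, not excluded. The primary outcome refers broadly to hospital data and billing forms, and nothing forbids the use of implant or imaging charges. That stands, and it rules out saying that the sponsor removed two costs. It does not rescue the plan: Appendix C never says such charges will be used, and nothing ensures that a scan done before admission appears on the form that is collected.

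Several stronger readings are tempting, and the documents do not support them.

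- *The comparison as a whole is tilted towards iTotal.* Only the CT part has a known sign. Assuming that the iTotal implant costs at least as much as the comparator would presuppose the answer.
- *The list holds only stay, readmission and operating-room items, with a cost window that opens at admission.* It also holds comorbidities and related adverse events, and no window is stated.
- *Every iTotal subject in the trial is affected.* The sub-study covers contracted US sites only.
- *The absence of CT from the visit schedule shows that it will not be costed.* The schedule sets out study assessments common to both arms, while the CT belongs to the making of the implant. Its absence shows only that no study visit captures it.

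The billing list also ends in a bullet without text, which may be an item lost when the document was read. Nothing here rests on it.

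A hospital perspective is also defensible, and who pays for the CT is not stated. If the hospital does not bear the scan, leaving it out could be right for that perspective. This is a reason to state the perspective. It also means that one particular start and end of the cost period cannot be demanded on this ground.

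**Conclusion.** The concern holds in a limited form. Appendix C promises a cost comparison without naming the one input that the protocol describes for iTotal alone, or the implant cost in either arm. Leaving out the CT understates iTotal cost by one CT per sub-study subject, at any CT price, under any perspective that bears the scan. The implant effect and the net direction are not established, because no prices are given; the range of -800 to +3,000 USD rests wholly on assumed values.

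The conclusion assumes that every iTotal implant needs a design CT, as Section 2 indicates, and that the off-the-shelf systems need none, since none is described. It bears on the credibility of a cost claim from an optional sub-study, and leaves the trial's efficacy and safety conclusions untouched.

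**What to change.** In Appendix C, before any cost data are examined:

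1. Add pre-operative planning imaging and implant and instrument cost to the cost components for both arms, valued by site charge or by one fixed tariff.
2. State the perspective (hospital, payer or other), so that it is clear who bears the CT and which encounters the billing forms must cover.
3. Report total cost with and without implant price, so that readers can see how far the result depends on it.

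If these inputs cannot be obtained, rename the analysis a comparison of hospital resource use and draw no cost conclusion from it.

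The cost is appendix wording and two further inputs per subject, which may have to be standardised values if actual prices are confidential. The result may be less favourable to iTotal. No visit, assessment or treatment needs to change.
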